12.1	FUNDING SOURCE	21
12.2	CONFLICT OF INTEREST	21
13	REFERENCES	21

List of Abbreviations

LIST OF ABBREVIATIONS

AE	Adverse Event
ALK	Alkaline phosphatase
AST	Aspartate aminotransferase (also SGOT)
CCA	Cholangiocarcinoma
CFR	Code of Federal Regulations
CRF	Case Report Form
DSMB	Data and Safety Monitoring Board
FDA	Food and Drug Administration
GCP	Good Clinical Practice
HIPAA	Health Insurance Portability and Accountability Act
IB	Investigator's Brochure
IND	Investigational New Drug Application
IRB	Institutional Review Board
LT	Liver transplantation
PHI	Protected Health Information
PI	Principal Investigator
PSC	Primary sclerosing cholangitis
SAE	Serious Adverse Event/Serious Adverse Experience
SOP	Standard Operating Procedure
UDCA	Ursodeoxycholic acid

Study Summary

Title	An Open-Label Pilot Study Evaluating the Safety and Efficacy of Oral Curcumin in Patients with Primary Sclerosing Cholangitis
Running Title	Curcumin in Patients with Primary Sclerosing Cholangitis
Protocol Number	14-002660
Phase	Phase I/II
Methodology	Open-label
Overall Study Duration	12-18 months
Subject Participation Duration	3 months
Single or Multi-Site	Single Site (Mayo Clinic in Rochester, MN)
Objectives	Determine the safety and efficacy of curcumin and whether it should be considered for further investigation in a randomized study with a larger number of patients.
Number of Subjects	15
Diagnosis and Main Inclusion Criteria	Patients with primary sclerosing cholangitis
Study Product, Dose, Route, Regimen	One 750 mg CuraMed® softgel (EuroPharma, Inc.) by mouth twice a day. Each 750 mg CuraMed® softgel supplies 500 mg of highly bioavailable BCM-95 curcumin.
Duration of Administration	12 weeks
Reference therapy	NA/no pharmacotherapy
Statistical Methodology	Mann-Whitney U test for continuous variables, Chi-square/Fisher's exact test for categorical variables.

1 Introduction

This document is a protocol for a human research study. This study will be carried out in accordance with the applicable United States government regulations and Mayo Clinic research policies and procedures.

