1.5 Dose Rationale and Risk/Benefits

In this pilot study, patients will receive 1500 mg of highly bioavailable BCM-95 curcumin®, which is supplied in one 750 mg CuraMed® softgel (EuroPharma, Inc.), to be taken orally twice a day for 12 weeks. Each softgel contains 500 mg of pure, highly bioavailable curcuminoids. This dose and route is based on recent published clinical trials, wherein curcumin has been found to be well-tolerated, safe, and efficacious in inflammatory and other disorders.^{12, 31-33, 35} Although previous studies have studied twice and three times a day regimens, we have chosen to

pursue the former given convenience and ease of adherence for patients and lack of inferiority data with this dosing regimen.

As described above, serious adverse effects have not been reported with even high doses (e.g. 10x higher than those used herein) of curcumin.^{14, 29} Mild adverse effects have been reported, however these have been uncommon and resolved with curcumin dose reduction or discontinuation.^{11-15, 29, 30, 36} These effects have included: yellow stool, diarrhea, headache, rash, increase in ALK or lactate dehydrogenase.)

2 Study Objectives

Primary Objective: to determine the change in serum Alkaline Phosphatase following 12 weeks of curcumin treatment as a biomarker of therapeutic efficacy.

Secondary Objective: to determine: 1) change in serum AST, total bilirubin, albumin, C-reactive protein, and Mayo PSC risk score following 12 weeks of curcumin treatment compared to baseline values as markers of biochemical improvement; 2) change in self-reported health status, fatigue severity, and pruritus (as assessed by standardized questionnaires) following 12 weeks of treatment compared to baseline values as markers of symptomatic improvement, and 3) the adverse events occurring during 12 weeks of curcumin treatment in patients with PSC.

3 Study Design

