3.2 Primary Study Endpoints

The primary study endpoint in this study will be treatment success, as determined by the proportion of PSC patients who experience clinically significant improvement in Alkaline Phosphatase, as defined by: 1) a $\geq 40\%$ reduction in serum Alkaline Phosphatase (as compared to baseline value)³⁷ or 2) a decrease in serum Alkaline Phosphatase to less than 1.5 times the upper limit of normal following 12 weeks of curcumin treatment.³⁸

Notably, serum Alkaline Phosphatase values have been repeatedly associated with disease response and prognosis,³⁹⁻⁴¹ thus this readily measured biochemical test is an important endpoint and biomarker in studies of patients with PSC.

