3.3 Secondary Study Endpoints

Secondary efficacy endpoints will include change in: 1) serum AST, total bilirubin, albumin, C-reactive protein, and Mayo PSC risk score⁴² following 12 weeks of curcumin treatment compared to baseline values as markers of biochemical improvement and 2) change in self-reported health status, fatigue severity, and pruritus (as assessed by standardized questionnaires) following 12 weeks of treatment compared to baseline values as markers of symptomatic improvement.

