5.3 Method for Assigning Subjects to Treatment Groups

This will be an open-label pilot study with one treatment group.

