7.1 Sample Size Determination

Approximately 5% of patients with PSC and chronically (>6 months) elevated ALK will spontaneously experience either a clinically significant reduction in serum ALK to less \leq 1.5 times the upper limit of normal³⁸ or a reduction of > 40% of the baseline ALK value.³⁷ In this open-label pilot study, our primary objective is to determine the proportion of patients who experience curcumin treatment success, as defined by either of these two ALK endpoints. Notably; these patients are hereinafter considered historical controls.³⁹ Therefore, if treatment success is achieved in at least 30% of curcumin treated patients, i.e. a rate that is at least 25% more than the conservative estimate in historical controls, likely based on pre-clinical data, and clinically promising, this would encourage further study of curcumin in larger, randomized clinical trials in patients with PSC.

By enrolling 15 patients with PSC in our study, an exact binomial test with a nominal two-sided significance level of $\alpha=0.05$ will have approximately 90% power to detect a 25% difference in clinically significant ALK improvement between the null hypothesis of 5% (historical control) and the alternative hypothesis of 30%. In addition, if 6 of 20 PSC patients (30%) experience treatment success, the 95% exact binomial confidence interval (CI) would be 11.9% to 54.3%, suggesting that the sample size has adequate precision to not include the null hypothesis (5%) in the CI.

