7.2 Statistical Methods

Univariate descriptive statistics and frequency distributions will be calculated, as appropriate, for all variables. Baseline values for demographic, clinical, and outcome variables (primary and secondary) will be tabulated. These analyses will help identify potential confounding variables to be used as covariates in advanced statistical (e.g. multivariate) analyses. Bonferroni correction will be used to adjust p-values in the case of multiple comparisons.

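### The only test named for continuous variables, Mann-Whitney U, compares two independent groups, but the trial has one group and its continuous outcomes are within-patient changes

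*Combined protocol and SAP*

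**What the plan says.** The Statistical Methodology line of the Study Summary gives the "Mann-Whitney U test for continuous variables" and, for categorical variables, Chi-square or Fisher's exact test. It ties neither test to an endpoint.

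Section 5.3 states: "This will be an open-label pilot study with one treatment group". The Summary lists no reference therapy.

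The continuous outcomes are all changes within the same patients:

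- Section 2 words the primary objective as "to determine the change in serum Alkaline Phosphatase following 12 weeks of curcumin treatment as a biomarker of therapeutic efficacy".
- Section 3.3 takes five measures (albumin, CRP, AST, bilirubin and the Mayo risk score) and looks at how each has changed: "following 12 weeks of curcumin treatment compared to baseline values as markers of biochemical improvement". It treats fatigue, pruritus and self-reported health status in the same way.

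Section 7.2 offers descriptive statistics, unspecified multivariate analyses and one multiplicity rule: "Bonferroni correction will be used to adjust p-values in the case of multiple comparisons". It names no test.

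The primary endpoint is handled separately. Section 3.2 makes it a proportion ("The primary study endpoint in this study will be treatment success, as determined by the proportion of PSC patients"), and Section 7.1 tests it by "an exact binomial test with a nominal two-sided significance level" of 0.05 against a historical rate of 5%.

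**The concern.** Mann-Whitney U needs two independent samples, and the plan describes no comparison that would supply them. There is no control arm, the historical controls enter only as a 5% response rate, and no subgroup comparison is specified. The planned Bonferroni adjustment shows that p-values are intended, yet the only test named for these outcomes cannot properly produce them.

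The obvious way to apply the Summary line is to treat the baseline and week-12 values as two groups. That discards the pairing. With positive correlation between a patient's two values, which is what one expects for these markers, the test becomes conservative and loses power. A real but moderate change in a secondary marker, or in ALK analysed as a continuous measure, could then be reported as non-significant. Because the study is open-label, leaving the test unsettled also allows it to be chosen after the data have been seen.

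**Working it through.** **What the documents fix.** One group; at most 15 patients; baseline and week-12 values on each; two-sided 0.05 (stated in 7.1 for the primary endpoint and carried over here); Bonferroni with no stated number of comparisons. No figure in the plan concerns the continuous outcomes, so there is none to reproduce.

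**What has to be assumed.** SD, within-patient correlation (rho), size of change and number of Bonferroni comparisons. For the last I take the eight outcomes of 3.3 (AST, bilirubin, albumin, CRP, Mayo score, health status, fatigue, pruritus), so alpha = 0.05/8 = 0.00625. At 0.05/10 power is 0 to 4 points lower with 15 pairs.

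**Model.** Log values are bivariate normal and standardised. The shift in SD units is -ln(1 - fall)/log-SD. At log-SD 0.5:

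- 20% fall: 0.223/0.5 = 0.45 SD
- 30% fall: 0.357/0.5 = 0.71 SD
- 40% fall: 0.511/0.5 = 1.02 SD

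A normal outcome on its original scale with the same shift gives the same result. P-values come from the exact null distributions of U (15 versus 15) and of the signed-rank statistic (15 pairs). There were 100,000 simulations per type I error cell and 20,000 per power cell.

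**Type I error at nominal 5%, 15 pairs**

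| rho | Mann-Whitney | Signed-rank |
|---|---|---|
| -0.3 | 7.5% | 4.7-5.0% throughout |
| 0 | 4.5% | |
| 0.3 | 2.0% | |
| 0.5 | 0.8% | |
| 0.7 | 0.15% | |
| 0.9 | under 0.01% | |

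Mann-Whitney exceeds 5% only at the negative correlation, which is unlikely for these markers.

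**Power at log-SD 0.5, 15 pairs, rho 0.5 / 0.7 / 0.9**

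| Fall | Alpha | Mann-Whitney | Signed-rank |
|---|---|---|---|
| 20% | 0.05 | 13 / 10 / 5% | 35 / 52 / 94% |
| 20% | 0.00625 | 2 / 1 / 0% | 10 / 19 / 68% |
| 30% | 0.05 | 42 / 42 / 44% | 71 / 90 / 100% |
| 30% | 0.00625 | 11 / 8 / 6% | 33 / 59 / 99% |

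With only 12 complete pairs, a 20% fall and alpha 0.05, the figures are 10 / 7 / 4% against 26 / 40 / 85%.

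**Where the loss is small.** For a 40% fall (rho 0.3 to 0.9, alpha 0.05, 15 pairs), Mann-Whitney keeps 77-100% power at log-SD 0.3 to 0.5. At log-SD 0.7 it has 44-48% against 58-100%. At alpha 0.00625 and log-SD 0.5 it has 40-41% against 52-100%. At rho = 0 the two tests are about equal: for a 0.5 SD shift both have 24%.

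**Limiting case.** Put 15 baseline log values at the normal quantiles (i - 0.5)/15 times the log-SD, and let every patient fall by exactly 20%. All 15 differences have the same sign, so the signed-rank p = 2/2^15 = 0.00006. The Mann-Whitney U is 158, 141 and 132 at log-SD 0.3, 0.5 and 0.7 (null mean 15 × 15/2 = 112.5), giving p = 0.061, 0.25 and 0.44. Even a uniform response in every patient is not significant at 5%.

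**The case against.** **The consequence is conditional.** The test appears in one summary line tied to no endpoint, and nothing proves that baseline and week-12 values will be treated as independent groups. That is so. But it is the only test named for continuous data, 7.2 does not override it, and no two-group comparison is planned for which it would be right.

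**The decision is little affected.** The 30% success criterion, of which 7.1 says "this would encourage further study of curcumin in larger, randomized clinical trials in patients with PSC", rests on the exact binomial test. The wording in 3.1 about what makes the study positive may refer only to that endpoint. With non-negative correlation the error is conservative and creates no false efficacy claim. All of this stands and limits the weight of the point.

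**The size rests on assumptions.** It does. The loss is slight for large effects with low variability, and the uniform-fall example is an extreme.

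**The signed-rank test is not a clean 5% test of drug effect on ALK.** Section 4.1 requires ALK above 1.5 times the upper limit, so baseline is selected on the outcome. If the analysed baseline is truncated at 0.5 SD below the mean and there is no treatment effect, signed-rank rejects in about 11%, 9% and 7% of trials at rho 0.7, 0.8 and 0.9. Truncation at the mean gives 20%, 15% and 10%; truncation at 1 SD below gives roughly 5-7%. The truncation point is assumed, and the six-month requirement may reduce the effect. This is regression to the mean, which any single-arm before-after comparison of ALK carries. It limits interpretation but gives no reason to keep a two-sample test.

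**Other paired methods would serve.** A paired t-test on logs is also defensible; the choice among paired methods is partly preference.

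**Conclusion.** The plan is wrong as written: the one test it names for continuous variables does not fit a single-group design with within-patient changes, and no suitable test is named elsewhere. This is a mismatch, not merely missing detail.

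It affects the continuous secondary outcomes and the ALK change in Section 2. It leaves the binary primary endpoint and the go-forward criterion untouched. The Summary's Chi-square/Fisher entry is a related mismatch, since 7.1 tests the success proportion by a one-sample exact binomial test.

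If the named test were applied to the paired values, the cost would be power. For moderate falls of 20-30% at log-SD 0.5 and rho of 0.5 or more, power at 5% would be 5-44% instead of 35-100%. That range depends on an assumed SD, correlation and effect, and on the test being used in that way. The point should be fixed; it does not undermine the primary analysis.

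**What to change.** In the Study Summary and Section 7.2, replace the Mann-Whitney entry with:

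> Week-12 and baseline values will be compared within patients by the Wilcoxon signed-rank test (on log values for ALK, AST, bilirubin and CRP; on the original scale for albumin, Mayo risk score and questionnaire scores). The median within-patient change and its 95% CI will be reported for all-treated patients (7.3) with both values, together with the number lacking a week-12 value.

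Add a sentence saying whether a sample taken at early termination counts as the week-12 value, because Section 6 schedules the two together. For ALK, note that the before-after p-value may partly reflect regression to the mean.

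In the Summary, name the one-sample exact binomial test of 7.1 for the success proportion in place of Chi-square/Fisher.

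The cost is wording in two places. The baseline and week-12 measurements are already scheduled in Table 1, so no extra patients, visits or data are needed. The analysis uses however many patients have both values: at most 15, and fewer after withdrawals.

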1.1 Background

Primary sclerosing cholangitis (PSC) is a chronic, fibro-inflammatory, cholestatic liver disease affecting approximately 25,000 adolescents and adults in the United States and a major indication for liver transplantation (LT).¹⁻³ PSC leads to end-stage cirrhosis, represents a foremost risk factor for CCA, and carries a median LT-free survival of only 12 years.⁴⁻⁷ The etiopathogenesis of PSC is unknown, and despite trials of nearly 20 different immunosuppressants and other agents, safe and effective pharmacotherapy has yet to be established.² Unlike in other cholestatic liver diseases (e.g. primary biliary cirrhosis), treatment with ursodeoxycholic acid (UDCA) has not been clearly shown to have a beneficial effect in PSC. In addition, high doses of UDCA have been associated with significantly greater adverse outcomes. Although operative treatment with liver transplantation (LT) is effective for PSC, it is available in limited specialty centers and only an option in select patients; even in suitable LT candidates, however, PSC and CCA can recur post-LT.⁸⁻¹⁰ Therefore, given the morbidity and mortality of PSC and the challenges associated with operative treatment, safe and effective pharmacotherapy is critically needed. Furthermore, the negative results of previous clinical trials highlight the need to consider targeting alternative pathophysiologic pathways.

Curcumin, the principal curcuminoid of the rhizome turmeric (*Curcuma longa*), is a naturally occurring compound with anti-inflammatory and anti-oxidant properties, among other potentially therapeutic effects.¹¹⁻¹⁶ In a recent study of the mdr2 knockout murine model of PSC, it was shown that as little as 4 weeks of oral curcumin treatment resulted in a significant decrease in serum liver enzymes as well as histologic disease, including sclerosing cholangitis, ductular proliferation, and fibrosis, all of which are pathologic hallmarks of PSC.^{17, 18} Furthermore, curcumin has been shown to decrease cholangiocyte (i.e. biliary epithelial cell) reactivity as well as hepatic myofibroblast activation (i.e. pro-fibrogenic function), both of which are key phenomena in the pathogenesis of PSC.^{17, 18} Therefore, there is promising animal model and cultured human cell line evidence that curcumin may represent a safe, effective, and low-cost therapy for patients with PSC.

1.2 Investigational Agent

Curcumin is an orange-red powder that is a mixture of 3 compounds— curcumin, demethoxycurcumin, and bisdemethoxycurcumin.

Forty to eighty-five percent of an oral dose of curcumin passes through the gastrointestinal tract unchanged. The bioavailability of curcumin is greatest in the colon. Hexahydrocurcuminol is the major biotransformed metabolite of curcumin. The major biliary metabolites are tetrahydrocurcumin and hexahydrocurcumin.

Curcumin has been shown in a growing number of *in vitro* and *in vivo* studies to demonstrate biological activity with a variety of potentially medicinal applications, e.g. anti-inflammatory, anti-oxidant, and chemopreventive (i.e. anti-cancer).¹¹⁻¹⁶ In clinical studies, it is generally administered orally in capsule form, 2-3 times per day.

1.3 Preclinical Data

Emerging insights into the etiopathogenesis of and potential therapeutic approaches for PSC have been facilitated by the growing use of relevant animal models, particularly the mdr2 knockout mouse.^{19, 20} Indeed, recent experimental evidence from this model has demonstrated that as little as 4 weeks of treatment with the naturally-occurring compound curcumin results in a significant reduction of serum liver enzymes as well as histologic disease, including sclerosing cholangitis, ductular proliferation, and fibrosis (i.e. pathologic hallmarks of PSC).¹⁷ In addition to the promising mdr2 knockout mouse model data, curcumin has been shown *in vitro* to decrease insult-induced human cholangiocyte reactivity (a characteristic feature in PSC cholangiocytes),^{2, 17, 21} attenuate human myofibroblast activation (manifested classically in PSC as peri-ductal “onionskin” fibrosis),^{17, 22} and suppress proliferation and induce apoptosis of human CCA cells (which could serve a vital chemopreventive role in PSC patients).^{2, 23, 24} Curcumin may also confer therapeutic benefits in PSC patients through other mechanisms, including its antimicrobial activity,^{16, 25} as microbiota have been implicated in the pathogenesis of PSC, and indeed 70% of patients with PSC have inflammatory bowel disease, a disorder associated with enteric microbial dysbiosis.^{2, 26-28}

1.4 Clinical Data to Date

Curcumin has demonstrated high tolerability, safety, and efficacy in multiple studies including randomized controlled trials involving healthy individuals as well as patients with a variety of hepatic and non-hepatic inflammatory, degenerative, malignant, neuropsychiatric, and other illnesses.^{11-15, 29-35} Collectively, these studies have demonstrated anti-inflammatory, hepatoprotective, anti-fibrotic, immunomodulatory, and anti-carcinogenic activities of curcumin. No significant toxicity has been reported following either acute or chronic administration of turmeric extracts at standard doses. In a minority of patients, mild side-effects as nausea, diarrhea, headache, somnolence, and contact dermatitis (with topical use) have been reported.^{11-15, 29, 30}

1.5 Dose Rationale and Risk/Benefits

In this pilot study, patients will receive 1500 mg of highly bioavailable BCM-95 curcumin®, which is supplied in one 750 mg CuraMed® softgel (EuroPharma, Inc.), to be taken orally twice a day for 12 weeks. Each softgel contains 500 mg of pure, highly bioavailable curcuminoids. This dose and route is based on recent published clinical trials, wherein curcumin has been found to be well-tolerated, safe, and efficacious in inflammatory and other disorders.^{12, 31-33, 35} Although previous studies have studied twice and three times a day regimens, we have chosen to

pursue the former given convenience and ease of adherence for patients and lack of inferiority data with this dosing regimen.

As described above, serious adverse effects have not been reported with even high doses (e.g. 10x higher than those used herein) of curcumin.^{14, 29} Mild adverse effects have been reported, however these have been uncommon and resolved with curcumin dose reduction or discontinuation.^{11-15, 29, 30, 36} These effects have included: yellow stool, diarrhea, headache, rash, increase in ALK or lactate dehydrogenase.)

2 Study Objectives

Primary Objective: to determine the change in serum Alkaline Phosphatase following 12 weeks of curcumin treatment as a biomarker of therapeutic efficacy.

Secondary Objective: to determine: 1) change in serum AST, total bilirubin, albumin, C-reactive protein, and Mayo PSC risk score following 12 weeks of curcumin treatment compared to baseline values as markers of biochemical improvement; 2) change in self-reported health status, fatigue severity, and pruritus (as assessed by standardized questionnaires) following 12 weeks of treatment compared to baseline values as markers of symptomatic improvement, and 3) the adverse events occurring during 12 weeks of curcumin treatment in patients with PSC.

3 Study Design

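### Section 2 words the primary objective as change in alkaline phosphatase, but the defined primary is a success proportion; the change itself has no specified estimate or suitable test

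*Combined protocol and SAP*

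**What the plan says.** Section 2 gives the primary objective as "to determine the change in serum Alkaline Phosphatase following 12 weeks of curcumin treatment as a biomarker of therapeutic efficacy". It names no summary measure and no test.

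Section 3.2 says: "The primary study endpoint in this study will be treatment success, as determined by the proportion of PSC patients who experience clinically significant improvement" in ALK. A patient succeeds with a fall of at least 40% from baseline or with a week-12 value below 1.5 × ULN. Section 7.1 restates the aim: "our primary objective is to determine the proportion of patients who experience curcumin treatment success". It bases the exact binomial test, the 5% null, the 30% alternative and the sample size on that proportion.

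Section 3.3 lists change in "serum AST, total bilirubin, albumin, C-reactive protein, and Mayo PSC risk score", followed by the questionnaires. The secondary objectives in Section 2 name the same laboratory measures. ALK is in neither list.

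Two general statements touch ALK as a continuous variable. Section 7.2 says: "Univariate descriptive statistics and frequency distributions will be calculated, as appropriate, for all variables". The Study Summary names a "Mann-Whitney U test for continuous variables". Section 3.1 calls the study positive if liver biochemistries improve significantly, without saying which measure or by which test. Table 1 schedules ALK at entry, week 3 and week 12.

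**The concern.** The phrase primary objective is attached to a continuous change in one section and to a binary composite in another. These are different quantities. A reader of Section 2 expects a mean or median ALK change with an interval, and nothing in the plan says how to produce one. AST, bilirubin, albumin, C-reactive protein and the risk score are at least named as change endpoints; the trial's main biomarker is not.

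At stake is how the result will be read. In an open-label, single-arm pilot, an ALK fall with few responders could be presented as positive under Sections 2 and 3.1 and as negative under Sections 3.2 and 7.1. The opposite can also happen. If the continuous analysis is left undefined, its scale, test and prominence can be chosen after the data are seen.

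**Working it through.** **1. The plan's own figure.** The only power statement, in Section 7.1, concerns the proportion: about 90% for 5% versus 30% with 15 patients, two-sided α = 0.05. Exact binomial tails, X ~ Bin(15, p):

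- Reject at X ≥ 4 (2.5% in the upper tail): P(X ≥ 4 | 0.05) = 0.0055; power P(X ≥ 4 | 0.30) = 70.3%.
- Reject at X ≥ 3 (minimum-likelihood two-sided test): P(X ≥ 3 | 0.05) = 0.0362; power 87.3%.
- With 20 patients and X ≥ 4: 0.0159 and 89.3%, which does match the stated figure.

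The gap between 15 and 20 patients is a separate matter. Two things matter here: no power or precision is stated for ALK change, and the protocol does not say which cutoff, 3 or 4 of 15, applies.

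**2. Does the named continuous test fit?** Mann-Whitney U compares two independent samples. Section 5.3 specifies one treatment group, so the only contrast is each patient's week-12 value against that patient's own baseline. That needs a paired method.

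**3. Can the two quantities disagree?** Two invented data sets of 15 patients, using only the Section 3.2 rule:

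- All start at 3 × ULN and fall by between 20% and 35%. Week-12 values lie between 3 × 0.65 = 1.95 and 3 × 0.80 = 2.40 × ULN, so there are 0 successes. Every change is a fall, so the exact two-sided signed-rank p = 2/2¹⁵ = 0.00006.
- Four start at 1.6 × ULN and fall 10% to 1.44 × ULN; the other eleven rise 5% and none of them succeeds. Successes are 4/15, with upper-tail p = 0.0055 against 5%. The mean change is (4 × (−10) + 11 × 5)/15 = +1%.

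**4. Illustrative power for a true 20% fall, n = 15.** The documents give no ALK SD and no baseline distribution, so all inputs here are assumptions.

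Paired t-test on log ALK: standardised change d = −ln(0.80)/SD = 0.223/SD.

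- SD 0.25: d = 0.893, power about 89%.
- SD 0.35: d = 0.638, power about 63%.

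Without assuming an SD, the detectable change with 15 patients is 0.78 SD at 80% power and 0.90 SD at 90%.

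Responder rule: baseline log-normal with log-SD 0.5, truncated below at the 1.5 × ULN entry limit; log change normal with mean ln(0.80); success if the change is at most ln(0.60) or the week-12 value is below 1.5 × ULN. The simulated success probability is put into the binomial tail:

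| Baseline median (× ULN) | SD 0.25, ≥4 | SD 0.25, ≥3 | SD 0.35, ≥4 | SD 0.35, ≥3 |
|---|---|---|---|---|
| 2.0 | 71% | 88% | 82% | 93% |
| 2.5 | 53% | 76% | 71% | 88% |
| 3.0 | 39% | 64% | 61% | 82% |
| 3.5 | 28% | 53% | 54% | 77% |

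At SD 0.25 the paired test is ahead throughout, by anything from about 1 to 61 points. At SD 0.35 the responder rule is usually ahead. Part of that lead is noise: with no drug effect, SD 0.35 and median 2.5 × ULN, about 14% of patients succeed by chance and the ≥4 rule passes about 14% of the time.

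**The case against.** An objective asks a question and an endpoint makes it measurable. On that view Section 3.2 simply answers Section 2: one limb of success is a dichotomised percent change in ALK, and because entry requires ALK above 1.5 × ULN, the other limb normally needs a fall too. Section 7.1 then calls the proportion the primary objective, gives it the only specified test and ties further study to a 30% success rate. ALK would be missing from Section 3.3 because it is already the primary variable. A threshold-based primary with cited cut-offs is a legitimate design for a go/no-go pilot.

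Most of this stands. The operative primary is not in doubt, and it need not be replaced. A reader might infer that ALK change will never be analysed. The documents do not support that: Section 7.2 promises descriptive statistics for all variables, and the success rule is itself computed from ALK change.

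What the objection does not remove is that Section 2 still names a different quantity, that Section 3.1 leaves the positive result undefined, and that no stated test suits a within-patient change.

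**Conclusion.** The concern holds as a misalignment and a gap in specification. Section 2 does not match Sections 3.2 and 7.1. Beyond generic description, ALK change has no defined estimate or valid inferential analysis. This rests on the text alone and on the single-arm design.

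It is not an error in the primary test. Nor do the documents show that dichotomising throws away most of the information, although a reader might infer this from the favourable rows of the table. The comparison depends on an SD, a baseline distribution and a cutoff that the plan does not fix. For a 20% fall, responder power ranges from about 28% to 93%, against 89% or 63% for the paired test. The supportable conclusion is that neither analysis is uniformly more powerful and that the two can disagree, so the role of each should be fixed in advance.

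**What to change.** - Reword the primary objective in Section 2 as the proportion with treatment success, as in Sections 3.2 and 7.1.
- In Section 3.1, tie a positive study to that same proportion and test.
- Add to the secondary objectives, Section 3.3 and Section 7.2 the within-patient change in ALK from baseline to week 12, with a paired analysis. One option is a paired test on log ALK, reported as geometric mean percent change with a 95% CI; a Wilcoxon signed-rank test is a reasonable alternative. Choose one beforehand and show week 3 as supporting data.
- In the Study Summary, replace Mann-Whitney U with the chosen paired method for changes from baseline.

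The cost is wording and one extra secondary analysis of data already scheduled. No visit or sample is added, and the sample size and primary test do not change.
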